3.10 Sample size

Providing VE estimates for each separate study is one of the objectives of this project. Therefore, the minimum sample size should be estimated for each study to obtain precise CVE/IVE estimates. The pooled analyses should not prevent study teams at the country level from including a large enough sample size to obtain exact estimates for each country-specific study.

• Each study site/country to specify the minimum sample size calculation.

Sample size estimation in VE estimation is different from sample size estimation in hypothesis testing. Rather than focusing on whether a VE estimation includes 0% or not, it is the precision of the estimate which is more important. For example, with a VE of 70%, a lower boundary confidence interval of 1% does not provide a very informative VE estimate, even if the confidence interval does not include 0%. It is more important to have a VE estimate that is precise around the point estimate of 70% (e.g. with a lower boundary of 50%). In fact, a low VE estimate, which can be the case in particular stratified analyses, needs a very large sample size to provide a VE estimate where the confidence interval does not include 0%. For example, if the true VE is 5–10%, then a study providing a lower boundary not including 0% would be unreasonably large.

The following sample size estimates focus on precision of the VE estimate (Table 5).

The odds ratio (OR) has confidence intervals that are symmetrical around the point estimate in the log scale. However, due to the properties of the OR, these are asymmetrical around the point estimate on the arithmetic scale. The length of the confidence interval of an odds ratio on the arithmetic scale will therefore always be shorter at the lower limit (which will never reach zero). When converted to VE (VE=1-OR), the length of the confidence interval will always be shorter at the upper limit. Hence, the focus is on the precision of the lower limit of the confidence interval, and for Table 6 below, a potential range of between 10 and 30% (or 0.1–0.3) has been selected for this limit. A case-to-control ratio of 1:1 is also assumed, including varying vaccine coverage among the source population between 30% and 90%, and varying VE (with the OR between 0.1 and 0.7).

Table 5. Sample size calculations

Lower CI boundary	Controls/ case	Detectable OR	Vaccine coverage in source population/co ntrols	Number of cases	Number of controls	IVE/CVE	CI
0.3	1	0.1	0.3	60	60	90	60–98
0.3	1	0.2	0.3	85	85	80	51–92
0.3	1	0.3	0.3	118	118	70	40–85
0.3	1	0.4	0.3	157	157	60	30–77
0.3	1	0.5	0.3	203	203	50	20–69
0.3	1	0.6	0.3	255	255	40	10–60
0.3	1	0.7	0.3	314	314	30	0–51
0.2	1	0.1	0.3	96	96	90	70–97
0.2	1	0.2	0.3	148	148	80	60–90
0.2	1	0.3	0.3	216	216	70	50-82
0.2	1	0.4	0.3	299	299	60	40–73
0.2	1	0.5	0.3	395	395	50	30–64
0.2	1	0.6	0.3	507	507	40	20–55
0.2	1	0.7	0.3	633	633	30	10–46
0.1	1	0.1	0.3	241	241	90	80–95
0.1	1	0.2	0.3	433	433	80	70–87
0.1	1	0.3	0.3	681	681	70	60–77
0.1	1	0.4	0.3	985	985	60	50-68
0.1	1	0.5	0.3	1 346	1 346	50	40–58
0.1	1	0.6	0.3	1 764	1 764	40	30–49
0.1	1	0.7	0.3	2 240	2 240	30	20–39
0.3	1	0.1	0.4	42	42	90	60–98
0.3	1	0.2	0.4		63	80	49–92
0.3	1	0.3	0.4	91	91	70	40–85
0.3	1	0.4	0.4	125	125	60	30–77
0.3	1	0.5	0.4	165	165	50	20–69
0.3	1	0.6	0.4	212	212	40	10–60
0.3	1	0.7	0.4	265	265	30	0–51
0.2	1	0.1	0.4	68	68	90	70–97
0.2	1	0.2	0.4	111	111	80	60–90
0.2	1	0.3	0.4	168	168	70	50–82
0.2	1	0.4	0.4	238	238	60	40–73
0.2	1	0.5	0.4	323	323	50	30–64
0.2	1	0.6	0.4	421	421	40	20–55
0.2	1	0.7	0.4	534	534	30	10–46
0.1	1	0.1	0.4	170	170	90	80–95
0.1	1	0.2	0.4	323	323	80	70–87
0.1	1	0.3	0.4	528	528	70	60–77
0.1	1	0.4	0.4	786	786	60	50–68
0.1	1	0.5	0.4	1 098	1 098	50	40–58
0.1	1	0.6	0.4	1 466	1 466	40	30–49
0.1	1	0.7	0.4	1 891	1 891	30	20–39
0.3	1	0.1	0.5	32	32	90	60–98
0.3	1	0.2	0.5	51	51	80	51–92
0.3	1	0.3	0.5	77	77	70	40–85
0.3	1	0.4	0.5	109	109	60	30–77

Lower CI boundary	Controls/ case	Detectable OR	Vaccine coverage in source population/co	Number of cases	Number of controls	IVE/CVE	CI
0.3	1	0.5	ntrols 0.5	148	148	50	20–69
0.3	1	0.6	0.5	193	193	40	10–60
0.3	1	0.0	0.5	246	246	30	0–51
0.3		0.7	0.5	51	51	90	70–97
	1						
0.2	1	0.2	0.5	90	90	80	60–90
0.2	1	0.3	0.5	142	142	70	50–82
0.2	1	0.4	0.5	208	208	60	40–73
0.2	1	0.5	0.5	289	289	50	30–64
0.2	1	0.6	0.5	384	384	40	20–55
0.2	1	0.7	0.5	495	495	30	10–46
0.1	1	0.1	0.5	129	129	90	80–95
0.1	1	0.2	0.5	262	262	80	70–87
0.1	1	0.3	0.5	447	447	70	60–78
0.1	1	0.4	0.5	687	687	60	50-68
0.1	1	0.5	0.5	983	983	50	40-58
0.1	1	0.6	0.5	1 337	1 337	40	30–49
0.1	1	0.7	0.5	1 751	1 751	30	20-39
0.3	1	0.1	0.6	26	26	90	60-98
0.3	1	0.20	0.60	45	45	80	50-92
0.3	1	0.30	0.60	71	71	70	40-85
0.3	1	0.40	0.60	103	103	60	30-77
0.3	1	0.50	0.60	143	143	50	20-69
0.3	1	0.60	0.60	191	191	40	10-60
0.3	1	0.70	0.60	247	247	30	0-51
0.3	1	0.10	0.60	41	41	90	70-97
0.2	1	0.10	0.60	78	78	80	60-90
0.2	1	0.30	0.60	130	130	70	50-82
0.2	1	0.40	0.60	197	197	60	40-73
0.2	1	0.50	0.60	280	280	50	30-64
0.2	1	0.60	0.60	380	380	40	20-55
0.2	1	0.70	0.60	497	497	30	10-46
0.1	1	0.10	0.60	104	104	90	80-95
0.1	1	0.20	0.60	229	229	80	70-87
0.1	1	0.30	0.60	410	410	70	60-78
0.1	1	0.40	0.60	651	651	60	50-68
0.1	1	0.50	0.60	953	953	50	40-58
0.1	1	0.60	0.60	1 322	1 322	40	30-49
0.1	1	0.70	0.60	1 760	1 760	30	20-39
0.3	1	0.10	0.70	23	23	90	60-98
0.3	1	0.20	0.70	43	43	80	50-92
0.3	1	0.30	0.70	71	71	70	40-85
0.3	1	0.40	0.70	108	108	60	30-77
0.3	1	0.50	0.70	153	153	50	20-69
0.3	1	0.60	0.70	207	207	40	10-60
0.3	1	0.70	0.70	272	272	30	0-51
0.3	1	0.70	0.70	36	36	90	70-97
0.2	1	0.10	0.70	75	75	80	60-90
		0.20	0.70	131	131	70	50-90
0.2	1						
0.2	1	0.40	0.70	205	205	60	40-73
0.2	1	0.50	0.70	298	298	50	30-64
0.2	1	0.60	0.70	412	412	40	20-55
0.2	1	0.70	0.70	548	548	30	10-46
0.1	1	0.10	0.70	90	90	90	80-95
0.1	1	0.20	0.70	219	219	80	70-87
0.1	1	0.30	0.70	413	413	70	60-78
0.1	1	0.40	0.70	676	676	60	50-68
0.1	1	0.50	0.70	1 015	1 015	50	40-58
0.1	1	0.60	0.70	1 435	1 435	40	30-49
0.1	1	0.70	0.70	1 941	1 941	30	20-39
0.3	1	0.10	0.80	22	22	90	60-98
0.3	1	0.20	0.80	47	47	80	50-92
0.3	1	0.30	0.80	82	82	70	40-85
0.3	1	0.40	0.80	128	128	60	30-77
0.3	1	0.50	0.80	187	187	50	20-69
0.3	1	0.60	0.80	259	259	40	10-60
0.3	1	0.70	0.80	344	344	30	0-51
0.3	1	0.10	0.80	35	35	90	70-97
0.2	1	0.10	0.80	82	82	80	60-90
0.2	1 1					70	50-90
U.Z	 	0.30	0.80	151	151	70	JU-02

Lower CI boundary	Controls/ case	Detectable OR	Vaccine coverage in source population/co ntrols	Number of cases	Number of controls	IVE/CVE	CI
0.2	1	0.40	0.80	245	245	60	40-73
0.2	1	0.50	0.80	365	365	50	30-64
0.2	1	0.60	0.80	514	514	40	20-55
0.2	1	0.70	0.80	694	694	30	10-46
0.1	1	0.10	0.80	89	89	90	80-95
0.1	1	0.20	0.80	241	241	80	70-87
0.1	1	0.30	0.80	477	477	70	60-78
0.1	1	0.40	0.80	808	808	60	50-68
0.1	1	0.50	0.80	1 242	1 242	50	40-58
0.1	1	0.60	0.80	1 789	1 789	40	30-49
0.1	1	0.70	0.80	2 458	2 458	30	20-39
0.3	1	0.10	0.90	30	30	90	60-98
0.3	1	0.20	0.90	71	71	80	50-92
0.3	1	0.30	0.90	129	129	70	40-85
0.3	1	0.40	0.90	208	208	60	30-77
0.3	1	0.50	0.90	310	310	50	20-69
0.3	1	0.60	0.90	437	437	40	10-60
0.3	1	0.70	0.90	591	591	30	0-51
0.2	1	0.10	0.90	48	48	90	70-97
0.2	1	0.20	0.90	124	124	0.8	60-90
0.2	1	0.30	0.90	238	238	0.7	50-82
0.2	1	0.40	0.90	397	397	0.6	40-73
0.2	1	0.50	0.90	605	605	0.5	30-64
0.2	1	0.60	0.90	868	868	0.4	20-55
0.2	1	0.70	0.90	1 190	1 190	0.3	10-46
0.1	1	0.10	0.90	121	121	0.9	80-95
0.1	1	0.20	0.90	361	361	0.8	70-87
0.1	1	0.30	0.90	751	751	0.7	60-78
0.1	1	0.40	0.90	1 311	1 311	0.6	50-68
0.1	1	0.50	0.90	2 061	2 061	0.5	40-58
0.1	1	0.60	0.90	3 022	3 022	0.4	30-49
0.1	1	0.70	0.90	4 216	4 216	0.3	20-39

The sample size estimates above are for the crude analysis and an adjusted analysis would require a higher sample size.

The sample size should also be respected for each population subgroup for which a sub (stratified) analysis (e.g. effect modification) is planned.

See also the Analysis section on sample size requirements for analyses.

3.11 Data

3.11.1 Datasets and coding

Some study sites may not be able to collect all information proposed above. Study sites should indicate which variables they can collect and which data source they will use in Annex 1: List of variables collected, definition and coding. Study sites can use the coding (variable names and values) as specified in Annex 1, or use their own coding. For the pooled analysis, if study site-specific coding is used, a database dictionary should be supplied alongside the data.

3.11.2 Data collection instrument and sources of information

Data are to be collected using a standardised questionnaire/data collection form. The source(s) of data may include:

- vaccination card/certificate;
- hospital medical records;
- · interview with patient or his/her family;
- communication with the patient or his/her family via mobile phone;
- interview with patient's treating/admitting physician or GP;
- interview with patent's pharmacist;
- vaccination register;
- laboratory records.
- > Each study site/country to define the sources of information used for each variable collected and the potential limitations.
- > Each study site using study site-specific coding to provide a data dictionary for pooled analyses.

3.12. Data management

3.12.1 Data collection, entry and storage at study site level

Web-based data collection methods or paper-based methods can be used. Data entry procedures will include checks to minimise data entry errors.

Information on antigenic, when available, and genetic analyses, including GISAID accession number, can be included in the epidemiological database or stored separately on an Excel spreadsheet (see Annex 2).

All data should be stored and processed in a way compliant with EU general data protection regulations (GDPR) [29].

- > Study sites to specify procedures of data collection and entry;
- > Study sites to specify methods of data storage and their compliance with the EU GDPR requirements;
- > Study sites to provide a codebook that includes the variable names, variable descriptions, and the coding of variable values (see also Annex 1).

3.12.2 Data checking and cleaning

Data checking will be carried out at the study site level. Summary and frequency tables as well as visual representations of appropriate variables are used to find illegal, implausible or missing values within the dataset. Checks for inconsistencies are carried out (e.g. date of swab before date of symptom onset). These values should be checked against the questionnaires or queried against the hospital record. Any missing data will be described.

Any changes or recoding to the data during the cleaning process (e.g. age to age groups) are documented and stored separately from the crude database. Guidance and/or example scripts for data cleaning can be provided if so desired.

Data checking is an iterative process (see Annex 3). After checking, data will be cleaned and stored separately from the source data. All changes to the data will be documented in scripts.

3.13 Analysis

3.13.1 Individual (country/study site level) analysis

The timing to conduct each interim analysis will depend on the time needed to achieve the appropriate sample size and regular updates are foreseen. This will depend mainly on the incidence of hospitalisation, COVID-19/influenza incidence, vaccination coverage, the recruitment strategy within hospital/s and the number of participating hospitals/services per hospital.

Cases and controls will be described by baseline characteristics. Patients will be described according to:

- sex;
- age group;
- time: month of symptom onset;
- COVID-19 (CVE)/influenza (IVE) vaccination status;
- absence/presence of at least one, presence of more than one high-risk condition;
- specific chronic conditions (e.g. diabetes, respiratory, cardiovascular diseases, immunodeficiency);
- pregnancy;
- vaccination status of other vaccines;
- respiratory co-infections (where available);
- severity (ICU, oxygen use, invasive ventilation, death);
- SARS-CoV-2 variant/influenza (sub)type and clade (where possible) for cases;
- vaccine product (for vaccinated cases).

A sample layout of this descriptive analysis is provided in Table 6 below.

Table 6. Example of descriptive table for cases and controls; COVID-19/influenza hospital-based vaccine effectiveness study, ECDC multi-centre study, 2023

Variables	iables Number of laboratory-confirmed COVID-19 (or influenza) cases/total n (%)		
Median age (IQR)	X	Х	
Missing	X	X	
Age groups (years)			
20–59	x/x (x)	x/x (x)	
60–79	x/x (x)	x/x (x)	
≥ 80	x/x (x)	x/x (x)	
Missing	X	X	
Sex			
Female	x/x (x)	x/x (x)	
Missing	X	X	
Days between onset of symptoms and swabbing			
0	x/x (x)	x/x (x)	
1	x/x (x)	x/x (x)	
2	x/x (x)	x/x (x)	
3	x/x (x)	x/x (x)	
4–7	x/x (x)	x/x (x)	
COVID-19/influenza vaccination	x/x (x)	x/x (x)	
Missing	X	X	
etc.			

This study is a case—control study (test-negative design). The measure of association is the odds ratio (OR). This can be estimated by logistic regression. An OR = 1 indicates no association between an exposure and the outcome. An OR > 1 indicates a potential risk factor, an OR < 1 indicates a potential protective factor, noting that the confidence interval around the OR helps with its interpretation.

For vaccination as a preventive factor, the CVE/IVE can be computed as CVE/IVE = (1 - OR)*100. A 95% confidence interval is computed around the point estimate.

Univariable analysis will be carried out to measure the CVE/IVE against being a laboratory-confirmed COVID-19/influenza SARI case. Stratified analyses (e.g. by sex and age group) can follow to better understand potential effect modifiers and confounders.

Prior to multivariable analysis, a model development strategy will be determined and included in the plan of analysis. In the final step, multivariable analysis will be carried out to take confounding factors and potential effect modifiers into account. This will provide adjusted ORs from which the CVE/IVE can be estimated using the formula above.

Output tables presenting CVE/IVE estimates

To present the results in the most transparent manner and to enable the reader to best understand the data, tables similar to the one illustrated below in Table 7 can be used (variables presented just to illustrate the output format). Useful information includes numbers of cases and controls (overall and vaccinated) and presentation of results for different models.

Table 7. Example of table displaying vaccine effectiveness against COVID-19/influenza adjusted for various co-variables overall and by age group, hospital-based COVID-19/influenza vaccine effectiveness ECDC multi-centre study, 2023

Clade/variant	Population included	Analysis scenarios/adjustments made	CVE (or IVE) (%)	(95% CI)
COVID-19	All ages	N (cases/ vaccinated; controls/ vaccinated)		
(or influenza)		Crude		
		Adjusted for onset date (cubic spline)		
		Adjusted for sex		
		Adjusted for chronic condition		
		Adjusted for age (cubic spline)		
		Adjusted for onset date, age (cubic spline)		
		Adjusted for onset date, chronic condition		
		Adjusted for onset date, age (cubic spline), chronic conditions, sex		
	20-59 years	N (cases/ vaccinated; controls/ vaccinated)		
		Crude		
		Adjusted for onset month, age (cubic spline)		
	60 years and over	N (cases/ vaccinated; controls/ vaccinated)		
		Crude		
		Adjusted for onset date, age (cubic spline), chronic condition, sex		

3.13.2 Sensitivity analyses

As sensitivity analyses, study sites can measure CVE/IVE:

- with different cut-offs of numbers of days between onset and swab;
- with different cut-offs of numbers of days between vaccination and symptom onset;
- with varying the post-vaccination periods (e.g. 7 days, 14 days, etc.) to be considered 'completely vaccinated' or 'partially vaccinated' (see Section 3.8.1);
- including, excluding, stratifying or adjusting by previous positive test status, and also by different delays between prior test and inclusion in the study:
- excluding patients testing positive prior to hospitalisation but negative in hospital;
- · using only controls positive to other respiratory viruses;
- excluding controls testing SARS-CoV-2 positive (IVE) or influenza positive (CVE), or adjusting by COVID-19 vaccination (see also Section 5.1.7);
- using different reference groups for VE estimation (e.g. for CVE: unvaccinated people, people vaccinated with a smaller number of doses, people vaccinated in the previous season).
- 3.13.3 Pooled analysis.

The higher sample size for the pooled analysis will provide more precision around the VE estimates. Data can be coded as outlined in Annex 1, or a codebook can be provided by the study teams that includes the variable names, descriptions and coding. The central hub will perform data cleaning and document and share any further data cleaning and analysis with all study coordinators to ensure it can be reproduced.

See Annex 2 for details of the pooled analysis plan. For the pooled data, interim analyses will be conducted during different periods, if appropriate, and according to the available sample size.

The timing to conduct each interim analysis will depend on the time needed to achieve the appropriate sample size. This will depend mainly on the incidence of hospitalisation, COVID-19/influenza incidence, vaccination coverage, the recruitment strategy within hospitals and the number of participating hospitals/services per hospital.

The pooled analysis will be carried out in a similar way to the site-specific analysis. Country or study site will potentially be included as a fixed effect, or as a random effect in a multi-level model. Statistical heterogeneity between study sites will be determined in a two-stage analysis using the Q-test and the I² index [30].

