3.5.5 SARI patients testing negative for SARS-CoV-2/influenza (test-negative controls)

A control will be defined as a hospitalised patient fulfilling the SARI case definition, with a respiratory sample negative for SARS-CoV-2 by PCR (for CVE) or a respiratory sample negative for influenza (for IVE) on admission to hospital.

It is advised that all sites test for both SARS-CoV-2 and influenza during the influenza season, as well as for all other respiratory viruses (as appropriate, depending on time of year), even if they are not participating in IVE. If this is not feasible, then during influenza season all samples that are negative for SARS-CoV-2 should also be tested for influenza (if not already tested at primary care level).

Controls that are negative by PCR but have Ct results suggestive of COVID-19⁶, and those with prior SARS-CoV-2 infection in the three months before admission, may be excluded as controls in sensitivity analyses (see Section 3.5.7 'Exclusion criteria').

- A study site/country measuring only CVE should indicate which testing strategy they will use (testing all samples for both SARS-CoV-2 and influenza, or only testing for influenza in those negative for SARS-CoV-2).
- > Each study site/country to indicate whether they can test for other respiratory viruses, only SARS-CoV-2 and influenza, or only SARS-CoV-2.

Other control groups (optional)

During periods when respiratory viruses are in low circulation, the number of SARI patients testing negative for SARS-CoV-2/influenza may be limited. Some sites may therefore wish to include other control groups, either in addition to SARI controls or as an alternative, and these must be recruited throughout the whole study period.

Examples of other control groups include:

- Patients testing PCR-negative to all respiratory viruses;
- Patients testing PCR-positive to respiratory viruses other than influenza (if IVE) or SARS-CoV-2, e.g. rhinovirus, respiratory syncytial virus (RSV), etc.; noting that patients with seasonal coronaviruses are excluded for CVE;
- Patients hospitalised with non-SARI related symptoms matched by time, age group and, if possible, underlying conditions:
 - Example source of hospitalised non-SARI cases: hospital wards admitting patients without COVID-19.
 Primary care: selection of GP patients belonging to the hospital catchment area and vaccination target
- group matched by time and age group:

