3.9.3 Information on swab and test results

For each patient, sites will collect information on:

- date of admission (to allow estimation of and stratification by time from onset to hospitalisation, and to measure length of hospital stay);
- date of discharge/death (to allow the length of hospital stay to be measured);
- date of swab or date sample obtained (to allow estimation of and stratification by delay from swab to onset);
- information on COVID-19/influenza test(s) performed and laboratory results:
 - type of influenza and/or COVID-19 test (PCR, rapid test)
 - result of influenza and/or COVID-19 test
 - including information on antigenic and genetic analysis, if available

Some studies will be carrying out testing for other respiratory viruses. Study sites can collect:

 test results from any other respiratory viruses (e.g. rhinovirus, RSV, enterovirus, adenovirus, human metapneumovirus, seasonal coronaviruses, etc.)

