5.1.7 Inclusion of influenza-positive controls for CVE and SARS-CoV-2-positive controls for IVE

A key prerequisite of the test-negative design is that the vaccination of interest does not affect the control group. However, there may be a strong correlation between those receiving influenza and COVID-19 vaccines, which would introduce bias. For example, if inclusion of SARS-CoV-2-positive controls artificially lowers the vaccine coverage among influenza test-negative controls, there would be a bias towards a lower IVE. Similarly, inclusion of influenza-positive controls in CVE may artificially lower the vaccine coverage among SARS-CoV-2 test-negative controls, biasing towards a lower CVE. The test-negative design would no longer be valid.

To account for this, analyses should be carried out excluding SARS-CoV-2 controls (IVE) and influenza controls (CVE), if adequate information is available [31]. These estimates can be compared with the primary analysis including SARS-CoV-2/influenza controls.

Sensitivity analyses will be conducted, excluding controls who are positive for influenza from CVE estimation and controls who are positive for SARS-CoV-2 from IVE estimation.

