 - considering those vaccinated <X days before onset of symptoms as unvaccinated (in the main analysis these records will be excluded);
 - including SARI patients testing positive for influenza/SARS-CoV-2 in the control group;
 - including SARI patients testing positive for influenza/SARS-CoV-2 in the case group;
 - including SARI patients whose influenza/COVID-19 vaccine status is unknown in the control group;
 - using, as a control group, only SARI patients testing positive for at least one non-influenza respiratory virus/non-coronavirus;
 - considering different restrictions according to swabbing delay (e.g. <14 days, <10 days, etc.);
 - considering the sensitivity and specificity of PCR;
 - based on assumptions of previous infections;
 - excluding participants who received antivirals ≤14 days prior to swabbing;
 - excluding all participants with lab-confirmed influenza/SARS-CoV-2 at any time after symptom onset, to reduce bias.
- This can then be repeated using RSV as a sham outcome (if multiplex results are available for any sites).
 There should be no association between COVID-19/influenza vaccination and RSV-positivity in the absence of confounding.

Time can be input as a variable in the model to assess whether it can be an effect modifier.

Minimum sample size

Sample sizes may be very small for some sub-analyses. Different criteria can be used to determine whether the sample size is large enough to obtain a valid measure of VE;

- there are at least 10–15 cases (or controls, whichever is smaller) in the sub-analysis for crude analyses and more for adjusted analyses (e.g. at least 10 for each parameter in the model);
- there are ≥5 records in each cell of the two-by-two table of case and vaccination status;
- the precision of the estimate does not span both -200% and 90% (uninformative).

With low sample size, approaches include collapsing categories, or modelling continuous variables in a different way (if applicable). Sensitivity analyses can be carried out using penalised logistic regression.

Use of propensity scores

To limit the number of co-variables to include in the multivariable model, **if sample size allows**, estimates will be built and adjusted based on propensity scores. Propensity scores can be defined as the conditional probability of receiving the vaccine given a number of observed co-variables.

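### The wording of the other-virus-positive control analysis (3.13.2, 3.5.5, Annex 2) permits influenza-positive controls for CVE, the patients who 5.1.7 says may bias CVE downward.

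*Protocol*

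**What the plan says.** Three places in the protocol describe this control group.

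- Section 3.13.2, site-level sensitivity analyses: "using only controls positive to other respiratory viruses". Nothing else defines the group there. Removing influenza-positive controls (CVE) or SARS-CoV-2-positive controls (IVE) is the next bullet, listed as a separate analysis.
- Section 3.5.5, optional control groups: "Patients testing PCR-positive to respiratory viruses other than influenza (if IVE) or SARS-CoV-2, e.g. rhinovirus, respiratory syncytial virus (RSV), etc". The same item adds that patients with seasonal coronaviruses are excluded for CVE. It says nothing comparable about influenza for CVE.
- Annex 2, pooled sensitivity analyses: "using, as a control group, only SARI patients testing positive for at least one non-influenza respiratory virus/non-coronavirus".

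Section 5.1.7 explains why the choice matters: "inclusion of influenza-positive controls in CVE may artificially lower the vaccine coverage among SARS-CoV-2 test-negative controls, biasing towards a lower CVE". It ties this to a possibly strong correlation between receipt of the two vaccines. It describes the primary analysis as retaining these controls, with their exclusion as a comparison.

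**The concern.** A control group restricted to patients with another confirmed virus is a check on the primary VE estimate. It can serve that purpose only if the other virus is not itself the target of a vaccine whose uptake goes with the exposure of interest. For CVE, influenza is such a virus.

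The restriction removes every control with no virus detected. If influenza counts as another virus, its share of the control group therefore rises above its share among all controls. A lower CVE in this analysis could then be taken as fragility of the primary result, when it reflects which patients were kept. Sites reading the phrase differently, and the pooled analysis under Annex 2, could also report different control groups under one label. That works against the comparability that a core protocol is meant to secure.

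**Working it through.** **Step 1. What the phrase means in the protocol.**

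| Place | Does 'other' virus include influenza for CVE? |
|---|---|
| 3.13.2 | Not stated |
| 3.5.5, optional control group | Yes, read literally: the condition (if IVE) attaches to influenza only |
| 3.9.15 | Yes: influenza is counted among the other viruses a site tests for |
| 3.5.5, site-testing line | No: sites state "whether they can test for other respiratory viruses, only SARS-CoV-2 and influenza, or only SARS-CoV-2", so other viruses are a third category |
| 3.9.3 | No: the examples run from rhinovirus to seasonal coronaviruses, without influenza |
| Annex 2, Stratified analysis | No: co-infection with influenza (CVE), with SARS-CoV-2 (IVE) and with other viruses (both) are listed apart |
| Annex 2, sensitivity list | Unclear: see below |

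The Annex 2 slash allows two readings. Either the virus must be neither influenza nor a coronavirus, or it must be non-influenza for IVE and non-coronavirus for CVE. The second again admits influenza for CVE. Asking for at least one such positive result also does not clearly remove a control co-infected with, say, RSV and influenza.

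**Step 2. IVE.** In the 3.5.5 item SARS-CoV-2 carries no condition, so it is excluded for both analyses. That text does not admit SARS-CoV-2-positive controls for IVE. Only the silence of 3.13.2 leaves room for them.

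**Step 3. Size for CVE, as an illustration.** The protocol gives neither the influenza share of these controls nor the correlation of the two vaccines, so every input is an assumption:

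- COVID-19 vaccine coverage in the source population: c = 50%
- true CVE: 50%
- IVE: 30–50%
- influenza vaccination in COVID-vaccinated patients: f1 = 70–80%
- influenza vaccination in other patients: f0 = 20–30%
- influenza-positive share of the controls: s

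Formulas:

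- coverage in influenza-positive controls: pf = c(1 − f1·IVE) / [c(1 − f1·IVE) + (1 − c)(1 − f0·IVE)]
- coverage in all controls used: pc = (1 − s)·c + s·pf
- observed CVE = 1 − (1 − CVE)·[c/(1 − c)] / [pc/(1 − pc)]

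With c = 50% and CVE = 50% the case odds of vaccination are 0.5.

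*Stronger correlation* (f1 = 0.8, f0 = 0.2, IVE = 0.5): pf = 0.30/(0.30 + 0.45) = 0.400.

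- s = 0.5: pc = 0.450, odds 0.818, OR = 0.5/0.818 = 0.611, CVE 39%.
- s = 0.15: pc = 0.485, odds 0.942, OR = 0.531, CVE 47%.

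*Weaker correlation* (f1 = 0.7, f0 = 0.3, IVE = 0.3): pf = 0.395/(0.395 + 0.455) = 0.465.

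- s = 0.5: pc = 0.482, odds 0.932, OR = 0.537, CVE 46%.
- s = 0.15: pc = 0.495, odds 0.979, OR = 0.511, CVE 49%.

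*No correlation* (f1 = f0): pf = c, so observed CVE is 50% at any s. *No influenza-positive controls* (s = 0): 50%.

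Widening the inputs to IVE 30–60% and f1/f0 from 60/30% to 80/20% gives 35–47% at s = 0.5.

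**The case against.** The strongest reply is that the protocol more often uses 'other respiratory viruses' for viruses beyond both SARS-CoV-2 and influenza, that the 3.5.5 examples are rhinovirus and RSV, and that 3.13.2 is shorthand for Annex 2. This is a fair account of the likely intent, and much of it stands. It does not remove the literal 3.5.5 definition or the usage in 3.9.15, and Annex 2 is not clear enough to settle the matter.

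Three stronger conclusions might be inferred, and the documents do not support them.

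- That sites testing only for SARS-CoV-2 and influenza would use wholly influenza-positive controls for CVE. The 3.5.5 site-testing line treats such sites as not testing for other viruses. On that usage they have no eligible controls for this analysis.
- That influenza-positive patients would make up most of the restricted controls. No passage gives their share. The one-half used above is an assumption.
- That IVE is affected equally. The 3.5.5 text excludes SARS-CoV-2 without condition.

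It can also be said that the separate exclusion analysis protects the reader. It does so in part. It removes influenza-positive controls from the full control set, and nothing says it is combined with the other-virus restriction. In the illustration, removing a 15% share moves CVE only from 47–49% to 50%. That small shift would not prepare a reader for 39–46% in the restricted analysis.

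Finally, the figures are crude. Adjustment for age, onset date and chronic conditions, as in the example models of Table 7, may absorb part of the correlation between the two vaccines.

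**Conclusion.** The point holds as a defect of definition. The text permits influenza-positive controls for CVE in an analysis where section 5.1.7 gives reason to keep them out, and the protocol's own usage is split on whether they belong.

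The direction, towards a lower CVE, follows from 5.1.7 and depends on receipt of the two vaccines being correlated. The size is not known from the documents. A true CVE of 50% showing as about 39–46% is an illustration that rests wholly on assumed coverage, IVE, vaccine correlation and a one-half influenza share. With uncorrelated vaccination the bias is zero.

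The consequence is limited. Section 3.13.2 is permissive, this is a sensitivity analysis, and the primary estimate is unaffected.

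**What to change.** Use one definition in 3.13.2, in the optional control group of 3.5.5, and in the Annex 2 sensitivity list. For example: controls positive for at least one respiratory virus other than SARS-CoV-2, influenza and (for CVE) seasonal coronaviruses, and negative for both SARS-CoV-2 and influenza; only at sites that test for such viruses.

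The requirement of negativity for both target viruses goes beyond the present Annex 2 text and also deals with co-infected controls. Annex 2 therefore needs the edit too, and is not simply the wording to copy.

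The cost is one sentence in three places, fewer controls in this sensitivity analysis, and none at sites that test only for SARS-CoV-2 and influenza.
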